6.0 EVALUATIONS AND ASSESSMENTS

6.1 Time and Events Table

Assessment	Screening 1	C1 D1 ^{1,2}	C1 D8 ²	C2 D1 ^{1,2,} 14	C3 D1 ^{1,2}	C4 D1 ^{1,2,} 14	C5 D1 ^{1,2}	C6 D1 ^{1,2}	C7 D1 ^{1,2}	C8 D1 ^{1,2,} 14	C9 D1 ^{1,2}	C10 D1 ^{1,2,} 14	C11 D1 ^{1,2}	C12 D1 ^{1,2}	EOT ³	FU ⁴
Informed consent ¹²	Х															
Medical History ⁵	Х														Х	
Prior cancer therapy ¹³	Х															
Physical exam & vital signs ^{5, 14}	Х	Х		Х	Х	Х	Х	Х	Х	Х	Х	Х	Х	Х	Х	
ECOG Performance Status	Х	Х		Х	Х	Х	Х	Х	Х	Х	Х	Х	Х	Х	Х	
CBC with differential ⁶	Х	Х	Х	Х	Х	Х	Х	Х	Х	Х	Х	Х	Х	Х	Х	
Serum Chemistries ⁷	Х	Х	Х	Х	Х	Х	Х	Х	Х	Х	Х	Х	Х	Х	Х	
Testosterone (males)	Х				Х		Х		Х		Х		Х			
ECG	Х															
Serum pregnancy Test ⁸	Х															
CT scan chest/abdomen ²	Х				X ²		X ²		X ²		X ²		X ²			
Brain MRI ²	Х				x ²			x ²			X ²			X ²		
Peripheral blood sample ⁹		X ⁹			X ⁹		X ⁹		X ⁹		X ⁹		X ⁹		X ⁹	
Tumor sample	x ¹⁰														X ¹⁰	
Adverse event 5, 14 assessment		Х	Х	Х	Х	Х	Х	Х	Х	Х	Х	Х	Х	Х	Х	
Patient Diary		Provide ¹¹	Review	Review	Review	Review	Review	Review	Review	Review	Review	Review	Review	Review	Review	
Concomitant Meds	Review	Review	Review	Review	Review	Review	Review	Review	Review	Review	Review	Review	Review	Review	Review	
Subsequent Therapy and Survival Status																Х
Brigatinib		See section 4.2 for brigatinib schedule and dose														

Key to Footnotes

¹ Within 28 days prior to Day 1 of brigatinib unless otherwise noted. If screening (baseline) hematology and serum chemistries were performed within 7 days of D1 of cycle 1, these do not need to be repeated.

 2 Unless otherwise noted, a window of 2 days will be applied to all study visits; for every other cycle tumor imaging starting with D1 of cycle 3, imaging may take place within 7 days prior to the study visit to accommodate holiday, weekends, and transportation issues. CT scan should be of the chest and abdomen. The pelvis should only be performed if there is evidence on metastatic disease in the pelvis.

Brain imaging MRI of the brain should be performed at baseline. In patients with known brain metastases MRI is performed every 3 cycles to assess for intracranial disease progression. Patients without brain metastases on screening MRI will undergo repeat brain imaging as clinically indicated or institutional standard (i.e. a specific interval is not mandated by the protocol). If patient cannot tolerate or has contraindication to brain MRI, a CT scan with and without contrast can be used.

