¹¹ On C1D1 provide the patient diary for use. D1 of all subsequent cycles patient diary is to be collected from previous cycle, reviewed with the patient, and a new diary provided.

¹² Patients in cohort A and B are brigatinib treatment naïve and receiving brigatinib at a standard dose. Patients in cohort C will have progressed on brigatinib and will be receiving a higher than the standard dose brigatinib. Depending on the institutional practice and policies this may require patients on cohort C to sign a "post-progression" treatment informed consent document.

¹³ Prior systemic therapy will be collected including number of prior ALK TKI's and names, prior chemotherapy treatment. The sites of disease progression (CNS, extra-CNS or both) and if the patient received local therapy (e.g. radiation therapy, SBRT, etc.) to site of disease progression between disease progression and enrollment in study (i.e. disease progression in brain and lungs, brain metastases treated with SBRT and lungs metastases or primary not)

¹⁴ Even day cycle visits not including Brain MRI imaging and are conducted (at treating physician's discretion) as telemedicine visits will not include standard clinic assessments (i.e., symptoms/adverse event, blood pressure and heart rate). To maintain data integrity, these missed assessments are to be noted in the EDC as deviations (planned) and indicate that visit was conducted remotely.

6.2 **Pre-Study Assessments**

The assessments required as part of screening can be completed in one or more visits, as long as the assessments are completed within the time frames listed in the Key to the Time and Events table.

Clinical evaluation: complete history, comprehensive physical examination (to include height and weight), vital signs, ECOG performance status

Laboratory studies:

- **Pregnancy Test**: Serum pregnancy test is required for all women of childbearing potential within 7 days prior to D1
- Hematology: CBC with differential
- Serum Chemistries: blood urea nitrogen (BUN), creatinine, bilirubin, ALT (SGPT), AST (SGOT), alkaline phosphatase, amylase, creatinine phosphokinase (CPK)
- Serum Testosterone: Limited to male patients

Cardiac studies: ECG

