6.3 Treatment Assessments

6.3.1 D1 each Cycle

Tests and procedures in this Section 6.3.1 are to be conducted during each Day 1 cycle visit. Sections 6.3.3 and 6.3.4 include additional assessments to be conducted during each Day 1 at specific numbered cycle visit (e.g., odd cycles, each third cycle visit).

Clinical evaluation: focused medical history on symptoms/adverse events, comprehensive physical examination (to include weight), vital signs, ECOG performance status

Laboratory studies:

- Hematology: CBC with differential
- Serum Chemistries: blood urea nitrogen (BUN), creatinine, bilirubin, ALT (SGPT), AST (SGOT), alkaline phosphatase, amylase, creatinine phosphokinase (CPK).
- Blood sample: A blood sample for ctDNA will be requested (mandatory); see section 6.6 and the laboratory study for additional details. (Cycle 1 Day 1 & Day 1 of every odd cycle- 3, 5, etc.).

Patient diary: Collect, review with patient, and provide patient with new diary. (C1D1- provide patient with initial diary)

Concomitant medications: Review any additions or deletions.

AE: Adverse events will be assessed according to the NCI CTCAE v. 4.0.

6.3.2 D8 Cycle 1

Clinical evaluation: focused medical history on symptoms/adverse events,

Laboratory studies:

- Hematology: CBC with differential
- Serum Chemistries: blood urea nitrogen (BUN), creatinine, bilirubin, ALT (SGPT), AST (SGOT), alkaline phosphatase, amylase, creatinine phosphokinase (CPK)

Patient diary: Review

Concomitant medications: Review any additions or deletions.

AE: Adverse events will be assessed according to the NCI CTCAE v. 4.0.

6.3.3 D1 Cycle 3 and every odd numbered cycle thereafter (Cycle 3, 5, 7, etc.)

Tumor measurement: Tumor imaging should remain consistent throughout study, and should include CT scans of chest and abdomen. Pelvis should only be done if there is known metastatic disease in the pelvis.

Laboratory studies:

• Serum Testosterone: Male patients only

Blood sample: A blood sample for ctDNA will be requested (mandatory); see section 6.6 and the laboratory study for additional details.

6.3.4 D1 Cycle 3 and every third cycle thereafter (Cycle 3, 6, 9, etc.)

Brain metastases: Brain MRI or CT scan with or without contrast should be done every 3 cycles (3 months) for patients with known brain metastases to evaluated for CNS disease progression.

6.3.5 D1 Cycle 2 and each non-imaging even numbered cycle thereafter (Cycle 2, 4 or 8, etc.)

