The safety profile of the Study Drug is well-known at this point of this research

CONFIDENTIAL

study and many patients may be demonstrating stable tolerance of the Study Drug. For these patients, at the treating physician's discretion, even numbered cycle visits that do not include imaging procedures (i.e., CT scan, Brain MRI) may be conducted as telemedicine visits. When standard clinic assessments (i.e., symptoms/adverse event, blood pressure and heart rate) are not conducted, to maintain data integrity, these missed assessments are to be noted in the EDC as deviations (planned) and indicate that visit was conducted remotely.

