6.7 Assessment of Safety

Any patient who receives treatment on this protocol should be evaluable for toxicity. The criteria used to assess safety (typically the National Cancer Institute (NCI) Common Terminology Criteria for Adverse Events (CTCAE) version 4.0. Please refer back to the Time and Events table for the schedule of AE assessment.

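### Optional even-cycle telemedicine visits drop the symptom/adverse-event review, which needs no clinic attendance, and the protocol sections disagree on whether it is dropped

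*Combined protocol and SAP*

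**What the plan says.** **The schedule.** Section 6.7 gives the Time and Events Table its authority: "Please refer back to the Time and Events table for the schedule of AE assessment". The relevant row in 6.1, "Adverse event 5, 14 assessment", is marked at C1D1, C1D8, Day 1 of cycles 2 to 12, and end of treatment. Footnote 14 is attached to this row and to the C2, C4, C8 and C10 columns.

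**The exception.** Footnote 14 states that "telemedicine visits will not include standard clinic assessments (i.e., symptoms/adverse event, blood pressure and heart rate", and has the missed items entered as planned deviations. Section 9.5.2 likewise says, without condition, that these items are not carried out at remote visits, and confines the option to limited situations. Section 6.3.5, headed "D1 Cycle 2 and each non-imaging even numbered cycle thereafter (Cycle 2, 4 or 8, etc", leaves the choice to the treating physician on the premise that "many patients may be demonstrating stable tolerance of the Study Drug". It then speaks conditionally: "When standard clinic assessments (i.e., symptoms/adverse event, blood pressure and heart rate) are not conducted", the omission is logged as a planned deviation.

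**The general rule.** Section 6.3.1 says: "Tests and procedures in this Section 6.3.1 are to be conducted during each Day 1 cycle visit". Its list includes a focused symptom/AE history and CTCAE v4.0 assessment. Its cross-reference reads "Sections 6.3.3 and 6.3.4 include additional assessments to be conducted during each Day 1 at specific numbered cycle visit" and does not name 6.3.5. Section 7.3 asks that non-serious AEs be documented at least monthly.

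**The use of the data.** Treatment-related AEs, including at different doses, are secondary objective 2.2.1. Endpoint 2.5.1 is investigator-assessed CTCAE.

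**The concern.** Blood pressure and heart rate may need attendance; an AE interview does not. The footnote treats all three alike, so it gives up information that the remote contact could supply.

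The places that govern this also disagree. A site that does ask about symptoms by phone can record the review as done under 6.3.5, but footnote 14 and 9.5.2 treat it as no part of the visit. Sites may record the same contact differently.

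At stake is how completely and how accurately in time non-serious symptomatic AEs are captured. This matters most in cohort C. Section 1.1 makes the safety and tolerability of 240 mg a stated aim there, and reports only 15 earlier patients at 240 mg daily, 300 mg daily or 120 mg twice daily. The argument in 6.3.5 that the safety profile is well known fits that cohort least, and no section excludes cohort C from the option.

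**Working it through.** The plan states no count of omitted assessments, so there is no figure to reproduce. The check is a count on the table plus day arithmetic.

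**Inputs**
- Cycle length: 28 days (4.3.1, 4.3.2).
- AE row and columns marked with footnote 14: table in 6.1.
- Uptake of telemedicine: not given, so results are shown as a range.

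**Nominal days.** Day 1 of cycle c falls on day 28(c − 1) + 1. This gives C1D1 = 1, C1D8 = 8, C2 = 29, C3 = 57, C4 = 85, C5 = 113, C7 = 169, C8 = 197, C9 = 225, C10 = 253, C11 = 281 and C12 = 309.

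**Number of assessments.** C1D1, C1D8 and C2D1 to C12D1 make 2 + 11 = 13 on treatment (14 with end of treatment).

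**Share omitted, marked columns only**

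| Remote visits | Omitted | Share |
|---|---|---|
| 1 | 1/13 | 8% |
| 2 | 2/13 | 15% |
| 3 | 3/13 | 23% |
| 4 | 4/13 | 31% |

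**Intervals between AE reviews**
- All reviews kept: 7, 21, then 28 each; maximum 28 days.
- C2 remote: C1D8 to C3D1 = 57 − 8 = 49 days.
- C4 remote: 113 − 57 = 56 days.
- C8 remote: 225 − 169 = 56 days.
- C10 remote: 281 − 225 = 56 days.

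One remote visit is enough to produce the long gap. If the 2-day visit window is read as plus or minus 2 days, each interval can be up to 4 days longer (28 becomes 32, and 56 becomes 60).

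**Four is not a ceiling on the text.** Footnote 14 excludes visits that include brain MRI, and 6.3.5 excludes visits with CT or brain MRI. CT falls on odd cycles. Footnote 2 mandates brain MRI every 3 cycles only for patients with known brain metastases. In other patients C6 and C12 carry no mandated imaging, so the wording could admit them although their columns are not marked. That gives 6/13 = 46%; the longest gap stays at 56 days.

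**First review after the dose step, cohorts A and B.** With the step to 180 mg on D8 as scheduled, the first AE review on that dose comes 29 − 8 = 21 days later. If C2 is remote and the review is dropped, it comes 57 − 8 = 49 days later.

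**The case against.** The strongest reply is that this is a disclosed and limited choice. It is optional, rests on the physician's judgment and stable tolerance, and each miss is flagged in the database and so visible at analysis. Section 7.3 is not suspended, so AEs can still be documented monthly with their dates. Blood counts and chemistries, including CPK, amylase and transaminases, carry no footnote 14 on their rows. In the earlier randomized phase 2 trial the most common treatment-related grade 3 or higher event in the 180 mg arm was raised CPK (10.9%), which is found by laboratory test. AEs are a secondary, descriptive endpoint.

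Most of this stands, and it limits the size of the point. It does not restore the dropped review: flagging a gap does not fill it, and 7.3 governs documentation, not asking the patient.

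The stable-tolerance condition does argue against a remote C2 visit in cohorts A and B, so the 49-day case may be uncommon. The protocol nevertheless names cycle 2 in the heading of 6.3.5 and marks its column. For cohort C, entry requires at least 4 weeks at 180 mg without drug-related toxicity above grade 2, but that does not show tolerance of 240 mg.

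Stronger readings are tempting and are not supported:
- **That AEs are lost.** They can be entered later with onset dates, and reporting of serious events is unchanged.
- **That footnote 14 flatly contradicts 7.3.** The two are in tension only, because 7.3 speaks of documentation.
- **That a third of assessments will be missed.** That needs a patient treated through C12 and seen remotely at all four marked visits.
- **That the response analysis is affected.** Tumor imaging and the two-stage rule are untouched.

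**Conclusion.** The point holds as a problem of AE ascertainment and of inconsistent wording. Footnote 14 and 9.5.2 omit the symptom/AE review at remote even-cycle visits; 6.3.5 is conditional, and 6.3.1 does not acknowledge the exception. For a patient with at least one such visit the interval between reviews rises from a nominal maximum of 28 days to 49 days (C2) or 56 days (any later one). Between 1 and 4 of 13 assessments are omitted on the marked columns, and up to 6 of 13 on the wording alone in patients without brain metastases. These figures assume nominal visit days and treatment through C12; actual uptake is unknown.

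The consequence is possible recall error or under-recording of non-serious symptomatic AEs in the descriptive summaries for objective 2.2.1, with most weight in cohort C. It should be corrected because the correction is cheap; it does not threaten the primary result.

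**What to change.** Remove the symptom/AE item from the omitted assessments in footnote 14, 6.3.5 and 9.5.2, and state in each:

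> At a telemedicine visit the symptom/AE review in 6.3.1 (CTCAE v4.0) is done by phone or video and recorded as done remotely. Items that need attendance (e.g. blood pressure, heart rate) are entered as planned deviations, and AEs that depend on them are assessed at the next clinic visit.

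In 6.3.1, leave the sentence on additional assessments as it is, because 6.3.5 removes assessments and would not belong in it. Add a separate sentence:

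> For exceptions at telemedicine visits see 6.3.5.

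With the review kept, the monthly documentation in 7.3 is met without further change, and the longest interval between symptom/AE reviews is nominally 28 days. Blood pressure and heart rate may still go unmeasured for up to 56 days, so the 28-day figure does not extend to AEs detected by them, such as hypertension and bradycardia.

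The cost is wording in four places and a few minutes of interview on a contact at which diary and concomitant-medication review are already scheduled. It adds no visit and changes no dose or treatment rule.

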6.3 Treatment Assessments

6.3.1 D1 each Cycle

Tests and procedures in this Section 6.3.1 are to be conducted during each Day 1 cycle visit. Sections 6.3.3 and 6.3.4 include additional assessments to be conducted during each Day 1 at specific numbered cycle visit (e.g., odd cycles, each third cycle visit).

Clinical evaluation: focused medical history on symptoms/adverse events, comprehensive physical examination (to include weight), vital signs, ECOG performance status

Laboratory studies:

- Hematology: CBC with differential
- Serum Chemistries: blood urea nitrogen (BUN), creatinine, bilirubin, ALT (SGPT), AST (SGOT), alkaline phosphatase, amylase, creatinine phosphokinase (CPK).
- Blood sample: A blood sample for ctDNA will be requested (mandatory); see section 6.6 and the laboratory study for additional details. (Cycle 1 Day 1 & Day 1 of every odd cycle- 3, 5, etc.).

Patient diary: Collect, review with patient, and provide patient with new diary. (C1D1- provide patient with initial diary)

Concomitant medications: Review any additions or deletions.

AE: Adverse events will be assessed according to the NCI CTCAE v. 4.0.

6.3.2 D8 Cycle 1

Clinical evaluation: focused medical history on symptoms/adverse events,

Laboratory studies:

- Hematology: CBC with differential
- Serum Chemistries: blood urea nitrogen (BUN), creatinine, bilirubin, ALT (SGPT), AST (SGOT), alkaline phosphatase, amylase, creatinine phosphokinase (CPK)

Patient diary: Review

Concomitant medications: Review any additions or deletions.

AE: Adverse events will be assessed according to the NCI CTCAE v. 4.0.

6.3.3 D1 Cycle 3 and every odd numbered cycle thereafter (Cycle 3, 5, 7, etc.)

Tumor measurement: Tumor imaging should remain consistent throughout study, and should include CT scans of chest and abdomen. Pelvis should only be done if there is known metastatic disease in the pelvis.

Laboratory studies:

• Serum Testosterone: Male patients only

Blood sample: A blood sample for ctDNA will be requested (mandatory); see section 6.6 and the laboratory study for additional details.

6.3.4 D1 Cycle 3 and every third cycle thereafter (Cycle 3, 6, 9, etc.)

Brain metastases: Brain MRI or CT scan with or without contrast should be done every 3 cycles (3 months) for patients with known brain metastases to evaluated for CNS disease progression.

6.3.5 D1 Cycle 2 and each non-imaging even numbered cycle thereafter (Cycle 2, 4 or 8, etc.)

The safety profile of the Study Drug is well-known at this point of this research

CONFIDENTIAL

study and many patients may be demonstrating stable tolerance of the Study Drug. For these patients, at the treating physician's discretion, even numbered cycle visits that do not include imaging procedures (i.e., CT scan, Brain MRI) may be conducted as telemedicine visits. When standard clinic assessments (i.e., symptoms/adverse event, blood pressure and heart rate) are not conducted, to maintain data integrity, these missed assessments are to be noted in the EDC as deviations (planned) and indicate that visit was conducted remotely.

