3.1 Inclusion Criteria for all cohorts

- **3.1.1** Locally advanced or metastatic NSCLC that has been cytologically or histologically confirmed
- **3.1.2** ALK positive status based on Clinical Laboratory Improvement Amendments (CLIA) or test approved for use in Canada. Diagnostic test may be based on ctDNA testing or based in tumor testing
- **3.1.3** ECOG PS ≤2
- **3.1.4** Age of \geq 18 years
- 3.1.5 Brain lesions may be used as target lesions if progressing, ≥10mm in longest diameter and if they were not previously treated with any of the following:
 - Whole brain radiation therapy (WBRT) within 3 months
 - Stereotactic radiosurgery (SRS)
 - Surgical resection
- **3.1.6** Availability of core biopsy of progressive lesion taken within 60 days prior to D1 of treatment under study therapy or willing to undergo tumor biopsy: NOTE: All subjects must consent to provide tumor blocks or slides.
 - If archival tissue is not available and biopsies to obtain fresh tumor tissue cannot be performed with minimal risk to the subject, subjects may be permitted to enroll on the study with prior approval of the Study PI.
 - In the situation the patient undergoes biopsy within 60 days prior to D1 and there is insufficient tumor tissue for the correlative science part of the protocol, the patient will be permitted to enroll on the study with prior approval of the study PI
 - In the situation the patient undergoes molecular testing or nextgeneration sequencing as part of standard care there must be sufficient tumor sample available for participation in the study (i.e. a next generation sequencing report is not sufficient for enrollment)
- **3.1.7** Recovered from toxicities related to prior anticancer treatment to ≤Grade 2 or baseline with the exception of alopecia
- **3.1.8** Have normal QT interval on ECG evaluation QT corrected Fridericia (QTcF) of ≤ 450 ms in males or ≤ 470 ms in females

3.1.9 Adequate organ function defined as:

Absolute neutrophil count (ANC)	≥1500/µL
Platelets	≥75,000/µL
Hemoglobin	$\geq 10 g/dL$
AST /ALT	\leq 2.5 x upper limit of normal (ULN); \leq 5 x ULN if liver metastasis
Total serum bilirubin	\leq 1.5 x ULN
Serum creatinine	\leq 1.5 x UNL
Serum amylase	\leq 1.5 x UNL

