6.8.1 Assessment of Disease-Tumor Measurement Based on RECIST 1.1

See the international criteria proposed by the Response Evaluation Criteria in Solid Tumors (RECIST) Committee, version 1.1 (Eur J Cancer 45;2009:228-247) for additional details on RECIST1.1.

Measurable disease will be defined as the presence of at least one measurable lesion that can be accurately measured in at least one dimension with the longest diameter a minimum size of:

- $\geq 10 \text{ mm}$ by CT scan (CT scan slice thickness no greater than 5 mm)
- 10mm caliper measurement by clinical exam (lesions which cannot be accurately measured with calipers should be recorded as non- measurable).
- 20 mm by chest x-ray.
- >10 mm by MRI scan (MRI scan slice thickness no greater than 5 mm)

For malignant lymph nodes to be considered pathologically enlarged and measurable, a lymph node must be ≥ 15 mm in short axis when assessed by CT scan (CT scan slice thickness recommended to be no greater than 5mm). At baseline and in follow-up, only the short axis will be measured and followed.

All other lesions, including small lesions (longest diameter <10mm or pathological lymph nodes with \geq 10 to <15 mm short axis) as well as truly non-measurable lesions, will be considered non-measurable. Lesions considered truly non-measurable include: leptomeningeal disease; ascites; pleural/pericardial effusion; inflammatory breast disease; lymphangitic involvement of skin or lung, abdominal masses/abdominal organomegaly identified by physical exam that is not measurable by reproducible imaging techniques.

All measurements should be recorded in metric notation, using calipers if clinically assessed. All baseline evaluations should be performed as close as possible to the treatment start and never more than 4 weeks before the beginning of the treatment. The same method of assessment and the same technique should be used to characterize each identified and reported lesion at baseline and during follow-up. Imaging based evaluation should always be done rather than clinical examination unless the lesion(s) being followed cannot be imaged but are assessable by clinical exam. Clinical lesions will only be considered measurable when they are superficial and ≥ 10 mm diameter as assessed using calipers (e.g. skin nodules). For the case of skin lesions, documentation

by color photography including a ruler to estimate the size of the lesions is recommended.

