6.8.2 Baseline Documentation of Target and Non-Target Lesions

All measurable lesions up to a maximum of 5 lesions total (and a maximum of two lesions per organ) representative of all involved organs should be identified as target lesions and will be recorded and measured at baseline.

Target lesions should be selected on the basis of their size (lesions with the longer diameter), be representative of all involved organs, but in addition should be those that lend themselves to reproducible repeated measurements.

A sum of the diameters (longest for non-nodal lesions, short axis for nodal lesions) for all target lesions will be calculated and reported as the baseline sum diameters. If lymph nodes are to be included in the sum, only the short axis is added into the sum. The baseline sum diameters will be used as reference to further characterize the objective tumor response of the measurable dimension of the disease.

All other lesions (or sites of disease) including pathological lymph nodes should be identified as non-target lesions and should also be recorded at baseline. Measurements are not required and these lesions should be followed as "present" or "absent", or in rare cases "unequivocal progression".

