6.8.3 Evaluation of Target Lesions using RECIST 1.1 Criteria

NOTE: In addition to the information below, also see section 4.3.2 in the international criteria proposed by the Response Evaluation Criteria in Solid Tumors (RECIST) Committee, version 1.1 for special notes on the assessment of target lesions.²⁵

Complete response (CR) –Disappearance of all target lesions. Any pathological lymph node (LN) (whether target or non-target) must have decreased in short axis to <10mm.

Partial response (PR) –At least a 30% decrease in the sum of the LD of the target lesions taking as reference the baseline sum LD.

Progressive Disease (PD)–At least a 20% increase in the sum of the LD of the target lesions taking as reference the smallest sum LD recorded since the treatment started including baseline if that is the smallest on study. In addition to the relative increase of 20%, the sum must also demonstrate an absolute increase of at least 5mm. The appearance of one or more new lesions also constitutes PD.

Stable disease (SD)—Neither sufficient shrinkage to qualify for PR nor sufficient increase to qualify for PD taking as references the smallest sum LD since the treatment started.

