6.8.5 Evaluation of Best Overall Response using RECIST 1.1 Criteria

The best overall response is the best response recorded from the start of the study treatment until the end of treatment provided the confirmation criteria are met. To be assigned a status of PR or CR, changes in tumor measurements must be confirmed by repeat studies that should be performed ≥ 4 weeks after the criteria for response are first met. If a CR/PR cannot be confirmed the original "response" should be considered stable disease. The best overall response will be defined according to the following table:

Overall Response First Time Point	Overall Response Subsequent Time Point	BEST Overall Response
CR	CR	CR
CR	PR	SD, PD, or PR ¹
CR	SD	SD provided minimum criteria for SD duration met, otherwise, PD
CR	PD	SD provided minimum criteria for SD duration met, otherwise, PD
CR	NE ²	SD provided minimum criteria for SD duration met, otherwise, NE^2
PR	CR	PR
PR	PR	PR
PR	SD	SD
PR	PD	SD provided minimum criteria for SD duration met, otherwise, PD
PR	NE ²	SD provided minimum criteria for SD duration met, otherwise, NE^2
NE	NE ²	NE ²

¹ If a CR is truly met at first time point, then any disease seen at a subsequent time point, even disease meeting PR criteria relative to baseline, makes the disease PD at that point (since disease must have reappeared after CR). Best response would depend on whether minimum duration for SD was met. However, sometimes 'CR' may be claimed when subsequent scans suggest small lesions were likely still present and in fact the patient had PR, not CR at the first time point. Under these circumstances, the original CR should be changed to PR and the best response is PR.

²NE=inevaluable

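### Do the offset CT and brain MRI schedules stop responses from being confirmed in patients with both brain and extracranial target lesions?

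*Combined protocol and SAP*

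**What the plan says.** **Imaging calendar.** CT follows the schedule headed "D1 Cycle 3 and every odd numbered cycle thereafter (Cycle 3, 5, 7, etc" (6.3.3). For brain imaging, 6.3.4 states that "Brain MRI or CT scan with or without contrast should be done every 3 cycles (3 months) for patients with known brain metastases", beginning at Cycle 3. The Time and Events table (6.1) marks CT at Cycles 3, 5, 7, 9 and 11 and brain MRI at Cycles 3, 6, 9 and 12. Both 6.3.4 and footnote 2 of the table give intracranial progression as the reason for the brain scans.

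**What counts as response.** Section 3.1.5 says "Brain lesions may be used as target lesions if progressing, ≥10mm in longest diameter", provided they had no prior radiosurgery or resection and no whole-brain radiation within 3 months. Under 6.8.2, lesions "representative of all involved organs should be identified as target lesions and will be recorded and measured at baseline". Section 6.8.3 defines partial response as "At least a 30% decrease in the sum of the LD of the target lesions taking as reference the baseline sum LD", which is one sum over all targets. Section 6.8.1 adds: "The same method of assessment and the same technique should be used to characterize each identified and reported lesion at baseline", and the same holds during follow-up.

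**Confirmation.** Under 6.8.5, tumour changes "must be confirmed by repeat studies that should be performed ≥ 4 weeks after the criteria for response are first met", and a response that cannot be confirmed becomes stable disease. In its table, a response followed by an inevaluable assessment gives "SD provided minimum criteria for SD duration met, otherwise, NE".

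**Use of the endpoint.** Section 8.2 stops a cohort with fewer than 2 responses in 20 patients and calls the treatment promising with at least 5 in 40.

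**The concern.** Chest and abdomen CT cannot re-measure a brain target, so a CT-only visit leaves the target sum incomplete. A patient with mixed targets who responds at Cycle 3 has a CT at Cycle 5 and an MRI at Cycle 6, but no scheduled visit with both until Cycle 9. Section 6.8.5 does not spell out what the confirming repeat must cover, or whether scans from neighbouring cycles may form one assessment.

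Investigators could then differ over the same patient at Cycle 5. One might carry the Cycle 3 brain measurement forward and confirm the response, another might score the visit inevaluable, and a third might order an extra MRI. The first course could confirm a response that a complete scan would not; the second could lose a real one. ORR is investigator-assessed and drives both decisions of the two-stage design, so in principle either error could reach the trial's conclusion.

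**Working it through.** **1. Calendar.** Inputs: 28-day cycles (4.3); CT at odd cycles from 3 (6.3.3); brain imaging at multiples of 3 (6.3.4).

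- Cycles with both: {3, 5, 7, 9, …} ∩ {3, 6, 9, 12, …} = {3, 9, 15, 21, 27, …}. Cycle 27 starts 26 × 28 = 728 days after Cycle 1 Day 1, at the edge of the two-year data capture (9.4).
- Cycle 3 to next CT (Cycle 5): 2 × 4 = 8 weeks.
- Cycle 3 to next MRI (Cycle 6): 3 × 4 = 12 weeks.
- Cycle 3 to next visit with both (Cycle 9): 6 × 4 = 24 weeks.
- Windows do not close the gap. With the Cycle 5 CT 2 days late and the Cycle 6 MRI 7 days early, the scans are still 28 − 2 − 7 = 19 days apart.

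The calendar part of the concern is right.

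**2. The plan's own design figures.** With continuation at ≥ 2 of 20 and success at ≥ 5 of 40, let X be the stage 1 responses and Y the responses among the 20 patients of stage 2. Then

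P(reject treatment) = P(X ≤ 1) + Σ P(X = x) · P(Y ≤ 4 − x), for x = 2, 3, 4.

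| True rate | Early stop | Reject at stage 2 | Total | Declared promising | Plan (early stop, total) |
|---|---|---|---|---|---|
| 5% | 0.736 | 0.223 | 0.959 | 0.041 | 0.74, 0.96 |
| 20% | 0.069 | 0.045 | 0.114 | 0.886 | 0.07, 0.11 |

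These agree with 8.2, including its stated power of 89%.

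**3. Responses lost to a longer wait.** Assume exponential response durations. Compared with complete confirmation at 8 weeks, a further wait of d weeks loses the share 1 − 0.5^(d / median in weeks).

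| Assumed median duration | 12-week reading (d = 4) | 24-week reading (d = 16) |
|---|---|---|
| 4 months | 15% | 47% |
| 6 months | 10% | 35% |
| 9 months | 7% | 25% |
| 12 months | 5% | 19% |
| 15 months | 4% | 16% |

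**4. Effect on the decision.** Let f be the share of patients with mixed targets and g the share of their responses lost. The documents give neither. The effective rate is 0.20 × (1 − f·g).

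| f (assumed) | g (assumed) | Effective rate | Power | Early stop |
|---|---|---|---|---|
| – | 0 | 0.2000 | 0.886 | 0.069 |
| 5% | 5% | 0.1995 | 0.885 | 0.070 |
| 10% | 7% | 0.1986 | 0.882 | 0.071 |
| 10% | 25% | 0.1950 | 0.872 | 0.076 |
| 15% | 40% | 0.1880 | 0.851 | 0.087 |

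The last row needs a median duration of about 5 months, the 24-week reading and no unscheduled MRI. Every row also overstates the loss, because g is derived for responses first seen at Cycle 3 but applied to all responses. As a rough check on f, the crizotinib-refractory phase 2 trial in 1.3.9 had 44/222 = 20% with measurable brain lesions, and 34/222 = 15% with measurable lesions and an active brain metastasis. That was a different population, and 3.1.5 narrows the group further.

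**5. The opposite error.** If carried-forward brain measurements inflate responses in this subgroup by a share h, the null rate becomes 0.05 × (1 + f·h). With f = 5%, h = 5%, type I error is 0.0415; with f = 15%, h = 20%, it is 0.0457, against 0.041 with no inflation.

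**6. What the text already settles.** Section 6.8.3 judges response on the sum over all targets, 6.8.1 fixes the method for each lesion, and 6.8.5 asks for the measurement changes to be confirmed. Together they imply that each target is re-measured by its own modality. Four weeks is a minimum with no maximum. The table in 6.8.5 pairs a first time point with a subsequent one, not necessarily the next, and best response runs to the end of treatment. A CT-only Cycle 5 therefore does not prevent a complete Cycle 9 from confirming a partial response.

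**The case for a change.** The strongest case for a change is that none of this is written as a rule for one-modality visits. Section 8.3 plans no special handling of missing values, and the inevaluable row of 6.8.5 can be read against the patient. Two edits would address it: moving the Cycle 6 brain scan to Cycle 5 for patients with brain targets, and stating in 6.8.5 what confirmation must cover.

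The absence of an explicit rule stands. The edits gain little, however.

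- **Moving the scan.** It makes Cycles 3 and 5 both complete, but the brain interval from Cycle 5 to Cycle 9 becomes 4 × 4 = 16 weeks, in patients whose brain targets were progressing at entry. It also puts patients with and without brain targets on different schedules within one intracranial PFS analysis (2.5.4). Later responders are helped only in part: a response first complete at Cycle 9 would still wait until Cycle 15 for a visit with both scans.
- **Writing the rule.** It would mostly restate what 6.8.1, 6.8.3 and 6.8.5 imply together. Section 6.8.1 also refers to the RECIST 1.1 publication for details. That source was not available here, so it cannot be shown that a rule for partial assessments is missing.

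The strict inevaluable reading also proves too much. If a CT-only Cycle 5 cancelled the response, nearly every Cycle 3 response in this subgroup would be lost, even though Cycle 9 offers a complete repeat. Finally, 6.3.3 says tumour imaging should stay consistent through the study and should include chest and abdomen CT. That wording leaves room for a brain scan at the same visit when a brain lesion is a target.

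**Conclusion.** No change is needed. The schedules do coincide only at Cycles 3, 9, 15 and 21 within the data-capture period, and the protocol does not say whether neighbouring scans may be combined. But no stated rule produces a wrong ORR or a wrong two-stage decision. The confirmation interval has only a lower bound, unscheduled brain imaging is not barred, and the definitions already point to re-measuring every target by its own method. Analysts can fill what remains sensibly.

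The effect cannot be quantified from the documents. On the 12-week reading, with 10% of patients having mixed targets and a 9-month median response duration (all assumed), power falls from 0.886 to 0.882. Across the assumed range it stays between 0.851 and 0.885, the lower figure requiring several unfavourable assumptions at once. Type I error stays at or below 0.046. Separate CT and brain-imaging intervals are a fair trade-off, and realigning them would exchange a small gain in confirmation for coarser intracranial follow-up.
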